11.4 Methods of Analysis

Response criteria are described in Section 12. A responder is defined as a patient who achieves a best response of PR or CR on the study. Response rates will be calculated as the percent of evaluable patients who are responders, and confidence intervals will be constructed using the Wilson score interval method.⁵⁴ Decision making for A'Hern design cohorts will follow rules described above.

Toxicity tables will be constructed to summarize the observed incidence by type of toxicity and grade. A patient will be counted only once for a given toxicity for the worst grade of that toxicity reported for that patient. Toxicity information recorded will include the type, severity, time of onset, time of resolution, and the probable association with the study regimen.

11.5 Evaluability for Response

Any eligible patient who is enrolled and receives at least one dose of protocol therapy will be considered evaluable for response. Any patient who receives non-protocol anti-cancer therapy during the response evaluation period will be considered a non-responder for the purposes of the statistical rule, unless they show an objective response prior to receiving the non-protocol anti-cancer therapy (in which case they will be considered a responder). Patients who demonstrate a complete or partial response confirmed by central review will be considered to have experienced a response. All other patients will be considered non-responders. Patients who are not evaluable for response evaluation may be replaced for the purposes of the statistical rule. All patients considered to have a response (CR or PR) must have imaging studies reviewed centrally at the COG. Centers will be notified by the COG about requests for scans of patients with stable disease. Preliminary assessment of activity using institutionally provided tumor measurements will be entered into CDUS quarterly. The central review by COG will be provided as the final reviewed assessment of response when such becomes available.

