8.2 Radiology Studies

8.2.1 Central Radiology Review for Response: Patients who respond (CR, PR) to therapy or have long term stable disease (SD) (≥ 6 cycles) on protocol therapy will be centrally reviewed. The Operations center will notify the site when a patient has met the criteria for review. The tumor disease evaluations to be submitted for review include baseline (prestudy) evaluations as well as all end of cycle tumor disease evaluations which occurred while the patient was on the subprotocol therapy study

8.2.2 Technical Details of Submission:

To ensure an adequate interpretation of FDG-PET and CT with contrast scans, scans transferred between the treating institutions and the Imaging and Radiation Oncology Core Group IROC RI (QARC) must be submitted in Digital Imaging and Communications in Medicine (DICOM) format. BMP files, JPG files, or hard copies (films) are unacceptable for adequate interpretation of PET and CT with contrast scans. Imaging studies must be submitted electronically as outlined in the following paragraph. The images will be made available to study radiologists and nuclear medicine physicians for central review. Submission of Diagnostic Imaging data in DICOM format is required.

Alternatively, the images and reports may be submitted via sFTP to IROC Rhode Island. Digital data submission instructions including instructions for obtaining a sFTP account, can be found at http://irocri.qarc.org. Follow the link labeled digital data. Sites using the Dicommunicator software to submit imaging may continue

to use that application.

Corresponding Radiology reports may be submitted along with the electronic submission via sFTP or may be emailed to [contact]. The COG operations center and IROC are available to assist with any queries regarding the corresponding radiology reports which should be included when the scans are submitted

Questions may be directed to [contact] or [contact].

IROC Rhode Island (formerly QARC) will facilitate the central reviews.

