11.3 Study Design

The primary cohort and any biomarker negative expansion cohorts defined below will employ single stage A'Hern designs of N=20 and N=10 respectively. The agent will be deemed worthy of further study in the relevant subset of patients (i.e. biomarker positive in any histology, biomarker positive in a particular histology, etc) if the decision rule is met. Operating characteristics are shown below.

Cohort	N	Decision Rule	Alpha	Power
Primary biomarker positive		≥ 3 responses	10%	90%

Histology-specific biomarker positive expansion cohorts will, by definition, be deemed worthy of further study, since they will have at least 3 responses. The table below shows 90% confidence intervals (Wilson method) for a range of observable response rates.

Cohort Size Observed Response Rate		90% Confidence Interval	
10	30%	13% - 56%	
10	40%	19% - 65%	
10	50%	27% - 73%	

11.3.1 **Primary Cohort**:

APEC1621M will evaluate a primary cohort of 20 mutation-matched ("biomarker positive") evaluable patients of any histology for the primary study aim of determining the objective response rate (CR/PR according to the response criteria in Section 12.3) to the agent. Using an A'Hern design⁵³ with alpha=10%, a sample of N=20 will provide 90% power to detect an improvement in response rate from 5%, if the treatment is ineffective, to 25% if the targeted therapy is sufficiently effective to warrant further study. If there are at least 3 responses out of 20 in the primary cohort, the biomarker/therapy match will be deemed a success.

11.3.2 Histology-Specific Biomarker Positive Expansion Cohorts:

If ≥ 3 patients in the primary cohort with the same histology show signs of objective response (CR/PR according to the response criteria in Section 12.3), a histology-specific biomarker positive expansion cohort will open after the primary cohort is completed to up to 7 evaluable patients for a total sample size of 10 evaluable biomarker positive patients with that histology. This will allow us to estimate more precisely the activity in biomarker positive patients of that histology. See

We will open up to 3 such expansion cohorts for biomarker positive patients (i.e., if 3 histologies have \geq 3 responses, we will open a total of 3 expansion cohorts as described above). Note that this can only happen if the response rate in the primary cohort is at least 45% (9/20) and there cannot be more than 21 additional evaluable patients in total for these expansion cohorts.

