12.3.1 Definitions

12.3.1.1 Evaluable for objective response:

Eligible patients who receive at least one dose of protocol therapy will be considered evaluable for response. Evaluable patients who demonstrate a complete or partial response confirmed by central review before receiving non-protocol anti-cancer therapy will be considered a responder. All other evaluable patients will be considered non-responders

12.3.1.2 Evaluable Non-Target Disease Response:

Eligible patients who have lesions present at baseline that are evaluable but do not meet the definitions of measurable disease and have received at least one dose of protocol therapy will be considered evaluable for non-target disease response. The response assessment is based on the presence, absence, or unequivocal progression of the lesions.

12.3.2 Disease Parameters

12.3.2.1 Measurable disease: Measurable lesions are defined as those that can be accurately measured in at least one dimension (longest diameter to be recorded) as ≥ 20 mm by chest x-ray, as ≥ 10 mm with CT scan, or ≥ 10 mm with calipers by clinical exam. All tumor measurements must be recorded in millimeters (or decimal fractions of centimeters).

Note: Tumor lesions that are situated in a previously irradiated area might or might not be considered measurable. If the investigator thinks it appropriate to include them, the conditions under which such lesions should be considered must be defined in the protocol.

- 12.3.2.2 Malignant lymph nodes: To be considered pathologically enlarged and measurable, a lymph node must be ≥ 15 mm in short axis when assessed by CT scan (CT scan slice thickness no greater than 5 mm). At baseline and in follow-up, only the short axis will be measured and followed.
- 12.3.2.3 Non-measurable disease: All other lesions (or sites of disease), including small lesions (longest diameter < 10 mm or pathological lymph nodes with ≥ 10 to < 15 mm short axis), are considered non-measurable disease. Bone lesions, leptomeningeal disease, ascites,

pleural/pericardial effusions, lymphangitis cutis/pulmonitis, inflammatory breast disease, and abdominal masses (not followed by CT or MRI), are considered as non-measurable.

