12.7.4 Evaluation of organ enlargement

Complete Response (CR): Regress to normal

Partial response (PR): Spleen must have regressed by >50% in length

beyond normal

Stable Disease (SD): No increase consistent with progression

Progressive Disease (PD): In the setting of splenomegaly, the splenic length must increase by 50% of the extent of its prior increase beyond baseline. If no prior splenomegaly, must increase by at least 2 cm from baseline.

New or recurrent splenomegaly

12.8 **Best Response**

Two objective status determinations of disease status, obtained on two consecutive determinations, separated by at least a 3 week time period, are required to determine the patient's overall best response. Two objective status determinations of CR before progression are required for best response of CR. Two determinations of PR or better before progression, but not qualifying for a CR, are required for a best response of PR. Two determinations of stable/no response or better before progression, but not qualifying as CR or PR, are required for a best response of stable/no response; if the first objective status is unknown, only one such determination is required. Patients with an objective status of progression on or before the second evaluations (the first evaluation is the first radiographic evaluation after treatment has been administered) will have a best response of progressive disease. Best response is unknown if the patient does not qualify for a best response of progressive disease and if all objective statuses after the first determination and before progression are unknown.

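### Section 11.5 accepts a single response shown before other anti-cancer therapy, while Sections 11.4 and 12.8 require two determinations, so the ≥3/20 count rests on contradictory responder rules

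*Combined protocol and SAP*

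**What the plan says.** The primary decision in Section 11.3.1 is: "If there are at least 3 responses out of 20 in the primary cohort, the biomarker/therapy match will be deemed a success". It points to Section 12.3 for the response criteria. Five places bear on who counts:

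- **Section 11.4** defines a responder as a patient whose best response is PR or CR.
- **Section 12.8** defines best response: "Two determinations of PR or better before progression, but not qualifying for a CR, are required for a best response of PR". The two determinations must be at least 3 weeks apart. Table 5 (12.8.1) puts a PR or CR with no second assessment in the category of not RECIST classifiable.
- **Section 11.5, second sentence**: a patient given non-protocol therapy is a non-responder "unless they show an objective response prior to receiving the non-protocol anti-cancer therapy (in which case they will be considered a responder".
- **Section 11.5, third and fourth sentences**: a CR or PR confirmed by central review counts as a response, and everyone else is a non-responder. No timing condition is attached.
- **Section 12.3.1.1**: "Evaluable patients who demonstrate a complete or partial response confirmed by central review before receiving non-protocol anti-cancer therapy will be considered a responder".

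Central review follows a reported response. Section 8.2.1 says: "Patients who respond (CR, PR) to therapy or have long term stable disease (SD) (≥ 6 cycles) on protocol therapy will be centrally reviewed". The confirmatory scan is due on the next consecutive cycle (footnote to the Section 8.1 table; Section 12.3).

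**The concern.** The second sentence of 11.5 is a special rule for patients who move to other therapy. On its wording it lets one response assessment suffice for the patients least likely to get a second one: under Section 7.1 other anti-cancer therapy ends protocol therapy, and the confirmatory scan is about one cycle away. Sections 11.4 and 12.8 ask everyone for two determinations. Within 11.5, the same sentence also omits the central agreement that the following sentences make necessary.

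Two gaps add to this. Section 12.3.1.1 does not say whether the response or the central review must come before other therapy. Section 12.8 has no cut-off at the start of other therapy, so a later scan could serve as confirmation of an earlier PR.

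With a threshold of 3 in 20, one such patient can settle the result when the count is near the threshold, and the choice of rule would then be made with the outcome known.

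**Working it through.** **Inputs.** From Section 11.3.1: n = 20, success at 3 or more responses, null rate 5%, target rate 25%, alpha 10%, power 90%. Not in the documents: q, the share of first-documented responders who start other therapy before a second assessment. I take q from 5% to 30% as an assumption.

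**1. The plan's own figures.** P(X ≥ 3) = 1 − Σ C(20,x) pˣ(1−p)²⁰⁻ˣ for x = 0, 1, 2.

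- p = 0.05: 1 − (0.3585 + 0.3774 + 0.1887) = 0.0755 with unrounded terms, inside the 10% ceiling.
- p = 0.25: 1 − (0.0032 + 0.0211 + 0.0669) = 0.9087, which agrees with the stated 90%.

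N = 20 is the smallest size that meets both limits; N = 19 with the same threshold has power 0.8887. What is unsettled is the event being counted.

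**2. The rules side by side.**

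| Case | 11.5, sentence 2 | 11.5, sentences 3–4 | 11.4 with 12.8 and Table 5 | 12.3.1.1 |
|---|---|---|---|---|
| One PR, centrally agreed; other therapy before the confirmatory scan; no second assessment | Responder | Responder, if agreement on one scan is enough | Not a responder (not classifiable) | Depends on what must come before therapy |
| Local PR before other therapy; central review rejects it | Responder | Non-responder | 12.8 does not name the reader | Non-responder |
| PR, other therapy, PR again, no progression | Responder | Responder if centrally agreed | PR; the later scan confirms | Depends on what must come before therapy |

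The first two rows are direct contradictions. The third shows the missing cut-off in 12.8.

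**3. How often the decision would differ.** Let the first-response rate be 25%, so that the confirmed rate is 0.25(1−q). The confirmed count can never exceed the first-response count, so the decisions differ with probability P(X ≥ 3 | 0.25) − P(X ≥ 3 | 0.25(1−q)).

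| q | Confirmed rate | P(X ≥ 3), confirmed | Decision differs |
|---|---|---|---|
| 5% | 0.2375 | 0.887 | 2.2% |
| 10% | 0.225 | 0.861 | 4.8% |
| 20% | 0.200 | 0.794 | 11.5% |
| 30% | 0.175 | 0.706 | 20.3% |

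The third column is also the power if 25% was meant as a first-response rate but confirmed responses are counted.

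**4. The other direction.** If 5% is the confirmed rate but first responses are counted, the rate counted is 0.05/(1−q). Alpha is then 0.085 at q = 5%, 0.097 at 10%, 0.110 at 15%, 0.126 at 20% and 0.168 at 30%. It passes 10% between q = 10% and q = 15%.

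**The case against.** The best defence reads 11.5 together with 11.4. A responder is defined by best response, and 12.8.1 makes best response depend on confirmation, so the exception in 11.5 would be a timing clause for a response that already qualifies. The patient with one PR is then simply a non-responder. This is how the section may have been meant, but the text does not secure it: Section 12.3 uses the term objective response for the first documentation, before the confirmatory scan.

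Several parts of the defence do stand, and they rule out stronger readings that a reader might infer:

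- *That three sections give rival rules for patients who start other therapy.* Section 12.8 never mentions such therapy. It applies only because 11.4 makes best response the responder definition.
- *That 12.3.1.1 excludes a patient with two PR scans who starts other therapy before the central read is returned.* That is one reading of an ambiguous sentence. The condition can equally attach to the response, and 11.5 treats the central read as final whenever it arrives. On that reading 11.5 and 12.3.1.1 can largely be reconciled.
- *That the chance of a reversed decision is the chance of a count next to the threshold.* Exactly 2 of 20 has probability 18.9% at a true 5% and 6.7% at 25%; exactly 3 has 6.0% and 13.4%. These show exposure only. A reversal also needs a patient in the disputed class, and any ≥3/20 rule is sensitive to one patient.
- *That the plan exceeds its 10% alpha.* That depends on an assumed share above about 10%, which the documents neither give nor imply.

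**Conclusion.** The point holds as a contradiction in the definition of the primary event. Section 11.5 counts a response shown before other therapy without a second assessment, against 11.4 with 12.8 and Table 5, and it contradicts itself on central review. The open timing in 12.3.1.1 and the missing cut-off in 12.8 are secondary gaps.

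The sample size, alpha and power are correct as stated. The size of the effect is conditional on q: small at a 5–10% share (decision differs in 2.2–4.8% of trials at a 25% first-response rate) and material at 20–30% (11.5–20.3%). Few patients may be affected. It should be fixed because the repair is cheap and the rule ought to be settled before any such patient is seen; nothing here undermines the design.

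**What to change.** Use one responder definition in 11.4, 11.5, 12.3.1.1 and 12.8, for example:

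*A responder is a patient whose initial and confirmatory assessments (12.8) both show CR or PR, are both dated before any non-protocol anti-cancer therapy, and are agreed by central review, whenever that review is completed. All other evaluable patients are non-responders, and assessments after non-protocol therapy do not count.*

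Delete the parenthesis in 11.5. Reconcile the confirmation interval, which is at least 3 weeks in 12.8 but at least 28 days in Table 1 of 12.4.3, because the definition relies on it.

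The cost is a wording change in these sections. The downside is that an unconfirmed response followed by other therapy no longer counts, so the observed response rate may be slightly lower. The 5% and 25% in 11.3.1 should then be understood as rates under this definition.

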11.6 Evaluability for Toxicity

All eligible patients who receive at least one dose of protocol therapy will be considered in the evaluation of toxicity.

11.7 **Progression free survival (PFS)**

Progression free survival will be defined as time from the initiation of protocol treatment to the occurrence of any of the following events: disease progression or disease recurrence or death from any cause. All patients surviving at the time of analyses without events will be censored at their last follow-up date.

PFS along with the confidence intervals will be estimated using the Kaplan-Meier method. Patients with local calls of disease progression (i.e. calls made by the treating institution), will be counted as having had an event, even if the central review does not declare progression. We will also report PFS based on central radiology review as a secondary analysis, if adequate number of disagreements in progressions exist between the treating institutions and the central radiology review to make such an analysis meaningful.

11.8 Gender and Minority Accrual Estimates

The gender and minority distribution of the study population is expected to be:

	Ethnicity				
Racial category	Not Hispanic or Latino		Hispanic or Latino		
	Female	Male	Female	Male	Total
American Indian/Alaska Native	0	0	0	0	0
Asian	1	1	0	0	2
Native Hawaiian or Other Pacific Islander	0	0	0	0	0
Black or African American	3	5	0	0	8
White	12	20	4	2	38
More than one race	1	0	0	0	1
Total	17	26	4	2	49

This distribution was derived from the demographic data for patients enrolled on recent COG Phase 2 trials.

12.0 EVALUATION CRITERIA

12.1 Common Terminology Criteria for Adverse Events (CTCAE)

The descriptions and grading scales found in the current version of the NCI Common Terminology Criteria for Adverse Events (CTCAE) will be utilized for AE reporting. All appropriate treatment areas should have access to a copy of the current CTCAEv5.0. A copy of the CTCAEv5.0 can be downloaded from the CTEP website (http://ctep.cancer.gov).

12.2 **Progression-Free Survival**

Progression-free survival (PFS) is defined as the duration of time from start of subprotocol treatment to time of progression or death, whichever occurs first.

Development of new disease or progression in any established lesions is considered progressive disease, regardless of response in other lesions – e.g., when multiple lesions show opposite responses, the progressive disease takes precedence.

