12.3 Response Criteria for Patients with Solid Tumors

See the table in Section 8.0 for the schedule of tumor evaluations. In addition to the scheduled scans, a confirmatory scan should be obtained on the next consecutive cycle following initial documentation of objective response.

As outlined, patients will be assigned to one of the following categories for assessment of response: a) solid tumor (non-CNS) and measurable disease (Section 12.4); b) neuroblastoma with MIBG positive lesions (Section 12.5); c) CNS tumor (Section 12.7); and d) lymphoma/histiocytosis (Section 12.8). Note: Neuroblastoma patients who do not

have MIBG positive lesions should be assessed for response as solid tumor patients with measurable disease.

Response and progression will be evaluated in this study using the revised Response Evaluation Criteria in Solid Tumors (RECIST) guideline (version 1.1) [Eur J Ca 45:228-247, 2009]. Key points are that 5 target lesions are identified and that changes in the largest diameter (unidimensional measurement) of the tumor lesions but the shortest diameter of malignant lymph nodes are used in the RECIST v 1.1 criteria.

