12.4 Response Criteria for Patients with Solid Tumor and Measurable Disease

12.4.1 **Evaluation of Target Lesions**

Complete Response (CR): Disappearance of all target and non-target

lesions. Any pathological lymph nodes (whether target or non-target) must have reduction in short axis to <10 mm. If immunocytology is available, no disease must be detected by that methodology. Normalization of tumor markers if elevated at study enrollment (for patients with

neuroblastoma).

Partial Response (PR): At least a 30% decrease in the sum of the

diameters of target lesions, taking as reference the

baseline sum diameters

Progressive Disease (PD): At least a 20% increase in the sum of the

diameters of target lesions, taking as reference the smallest sum on study (this includes the baseline sum if that is the smallest on study). In addition to the relative increase of 20%, the sum must also demonstrate an absolute increase of at least 5 mm. (Note: the appearance of one or more new lesions is also considered progressions). Note: in presence of SD or PR in target disease but unequivocal progression in non-target or nonmeasurable disease, the patient has PD if there is an overall level of substantial worsening in nontarget disease such that the overall tumor burden has increased sufficiently to merit

discontinuation of therapy

Stable Disease (SD): Neither sufficient shrinkage to qualify for PR nor

sufficient increase to qualify for PD, taking as

reference the smallest sum diameters while on study

12.4.2 **Evaluation of Non-Target Lesions**

Complete Response (CR): Disappearance of all non-target lesions and

normalization of tumor marker level. All lymph nodes must be non-pathological in size (<10 mm

short axis)

Note: If tumor markers are initially above the upper normal limit, they must normalize for a patient to be considered in complete clinical

response.

Non-CR/Non-PD: Persistence of one or more non-target lesion(s)

and/or maintenance of tumor marker level above

the normal limits

Progressive Disease (PD): Appearance of one or more new lesions and/or

unequivocal progression of existing non-target lesions. Unequivocal progression should not normally trump target lesion status. It must be representative of overall disease status change,

not a single lesion increase.

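### For RECIST-assessed tumors, Section 12.2 defines progression for PFS lesion by lesion, while Section 12.4 defines it on the sum of target diameters and on overall non-target change

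*Combined protocol and SAP*

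**What the plan says.** Section 12.2 defines PFS as time from the start of treatment to progression or death. It then says what progression is: "Development of new disease or progression in any established lesions is considered progressive disease, regardless of response in other lesions". Its example is also about individual lesions: "when multiple lesions show opposite responses, the progressive disease takes precedence". The paragraph sets no minimum growth and is not limited to any tumor type.

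For solid tumors, Section 12.3 says: "Response and progression will be evaluated in this study using the revised Response Evaluation Criteria in Solid Tumors (RECIST) guideline (version 1.1"). Section 12.4.1 then defines PD for target lesions as "At least a 20% increase in the sum of the" diameters, measured from the smallest sum on study, and adds that "the sum must also demonstrate an absolute increase of at least 5 mm". PR is "At least a 30% decrease in the sum of the" diameters from baseline. For non-target lesions, Section 12.4.2 says of unequivocal progression: "It must be representative of overall disease status change", and "not a single lesion increase".

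Section 11.7 counts a progression call by the treating institution as a PFS event even where central review does not agree. Section 10.1a refers to Section 12 as a whole for progression as a reason to stop protocol therapy. The documents do not say which of 12.2 and 12.4 prevails where they differ.

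**The concern.** For non-CNS measurable disease, the plan describes progression of established lesions in two ways. Section 12.2 looks at each lesion by itself. Section 12.4 looks at the target lesions together and at the non-target lesions as a whole. A patient whose lesions move in different directions can have progressed under one section and not under the other.

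What is at stake is the secondary aim in 1.2.1, the estimate of PFS. Section 12.2 is the endpoint's own definition and local calls are final for the main analysis, so two sites reading different sections of Section 12 could record different event dates from identical scans.

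**Working it through.** There is no stated figure to reproduce; the question is whether the two rules give the same answer on the same scans.

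**Inputs.** From 12.4.1:
- PD: sum at least 20% above the smallest sum on study, and at least 5 mm above it.
- PR: sum at least 30% below baseline.
- SD: neither.

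From 12.2: progression in any one established lesion is PD. Because 12.2 gives no threshold, I assume the stricter version, that a single lesion has progressed only if it grows by at least 20% and at least 5 mm. The diameters below are assumptions chosen for illustration. Non-target disease is taken as not progressing, with no new lesions.

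**Formulas.** Change in sum = (sum now − reference sum) / reference sum. Change in lesion = (diameter now − reference diameter) / reference diameter.

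**Case A, shrinking sum.** Targets 50 + 20 = 70 mm become 20 + 26 = 46 mm.
- Sum: (46 − 70) / 70 = −34.3%. This is PR at that assessment under 12.4.1.
- Second lesion: (26 − 20) / 20 = +30%, or +6 mm. This is PD under 12.2.

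**Case B, nearly unchanged sum.** Targets 40 + 30 + 20 = 90 mm become 40 + 30 + 26 = 96 mm.
- Sum: 6 / 90 = +6.7%. The 5 mm condition is met but the 20% condition is not, so this is SD under 12.4.1.
- Third lesion: +30%, +6 mm. This is PD under 12.2.

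**Case C, growth after a response.** Targets 50 + 20 = 70 mm fall to 20 + 20 = 40 mm, then become 20 + 26 = 46 mm.
- Against the smallest sum: 6 / 40 = +15%, so not PD under 12.4.1. Against baseline: (46 − 70) / 70 = −34.3%, so still PR.
- Second lesion against its smallest value: +30%, +6 mm. This is PD under 12.2.

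**Non-target lesions.** If one non-target lesion enlarges unequivocally while overall disease status does not change, 12.2 makes it PD and 12.4.2 does not.

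**Where the rules agree.** New lesions are PD under both sections. With a single target lesion and the thresholds assumed above, the two target rules coincide, because the lesion is the sum. The conflict is confined to growth of established lesions in patients with more than one lesion.

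**The case against.** The best answer is that 12.2 is not a rival definition. It has no threshold, so it must borrow the meaning of progression from the disease-category criteria, and 12.3 names RECIST 1.1 for these patients. Read that way, 12.2 only says that progression outranks response. That matches Table 1 in 12.4.3, where PD in target or non-target disease makes the overall assessment PD. The same sentence also appears in the CNS criteria (12.6.4) beside a rule based on the sum of products, which suggests that the authors saw no conflict with a sum-based rule.

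This reading is possible, and it is probably close to what was intended. It does not fit the text of 12.2, which speaks of individual lesions and of several lesions moving in opposite directions, not of target and non-target categories. A site could apply it literally. Two parts of the objection do stand. The single-lesion exclusion in 12.4.2 concerns non-target lesions only and is worded as what should normally hold, not as an absolute. And some local progression calls will rest on clinical judgment without imaging (8.1, 10.1a), where neither rule is applied.

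Two stronger inferences are tempting. A reader might infer that 12.2 changes responder status, and so the primary endpoint, directly. The documents do not support that: overall response is built from the 12.4 categories (12.4.3), best response from the sequence of those assessments (12.4.4), and a responder needs central confirmation (11.5, 12.3.1.1). The only link is that 12.8 requires the two response determinations to come ahead of progression without saying which definition applies, as Case C would test.

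A reader might also infer a rate of false progression from measurement error under a lesion-by-lesion rule. That requires a per-lesion cut-off, a measurement SD, and the number and size of lesions to be measured, none of which is given in a form that fixes the rate. It would also depend on whether a 5 mm floor is read into 12.2: 20% growth reaches 5 mm only from 25 mm upward (0.20 × 25 = 5).

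**Conclusion.** The inconsistency is real for non-CNS measurable disease. As written, the same scans can be a PFS event under 12.2 and PR or SD under 12.4, and 11.7 carries a site's choice straight into the Kaplan-Meier estimate. The three cases show this even when a 20% and 5 mm threshold is granted to 12.2; with no threshold, the gap would be wider.

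The effect on PFS is direct. An effect on best response is possible only through the wording of 12.8. How many patients would be affected cannot be stated: the documents give no rate of mixed response, and the diameters here are illustrative. This is a definition worth correcting for a secondary endpoint, not evidence that the primary analysis fails.

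**What to change.** In 12.2, state that for the PFS endpoint, progression is determined by the criteria of the patient's disease category (Section 12.4, 12.5, 12.6 or 12.7), and limit the any-lesion sentence accordingly. It would help to add in 11.7 that local progression calls are made on those same criteria.

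Because 10.1a relies on Section 12 as a whole, the sponsor must also reconcile these passages for removal from therapy. Otherwise a patient could leave therapy on one reading with no PFS event recorded on the other. No position is taken here on which rule should govern stopping of treatment.

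The endpoint change costs one or two sentences. It needs no new data, scans or patients, and leaves the primary design unchanged.
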